6.3 Follow-up Phone Call Visits

Two days and seven days after the patient's final study visit, the study team will contact them to ask if they have had any unusual symptoms since their last visit. If patients answer yes, they may be asked to return to the clinic for an exam to determine if the symptoms are due to the study treatment.

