	
study medication and instructed how to apply it to the exposed area. When the patient first senses the start of developing a cold sore and applies study medication will be considered Day 1. Dosing of the study product will be done five times daily, beginning at the time that a subject first senses the start of the prodromal phase (Day 1). Subjects will be given a diary card to record their pain levels, progression of lesion development and any unusual symptoms (not normally seen with their outbreaks).
 
Patients will be called daily by the study team after their induction visit to determine the start of prodrome. If after 7 days, the patient does not develop any prodromal senses, the patient will be considered an induction failure.
 
When the patient first senses signs or symptoms of a cold sore, they will have the Day 1 visit conducted within 24 hours. Day 1 visit may be conducted in person or as a MyChart Virtual Visit. Their diary card will be reviewed and if they have experienced a prodrome and/or lesion since the induction visit, their compliance with dosing will be checked. If the subject has noted any unusual symptoms, these will be discussed with medical personnel to determine if the symptoms represent a treatment emergent AE. A photo will be taken of the irradiated area (as marked at the induction visit). The blinded assessor will assess the prodrome and/or lesion and take measurements.
 
On Days 3, 5, and 7, the subject will return to the clinic or follow up via virtual video call for assessment of the irradiated area. Study staff will review the subject diary to determine if the subject is correctly noting the lesion stage. Subjects will have a photo taken of the radiated area and asked to continue with dosing as instructed. Any diary card notation of unusual symptoms in subjects will be reviewed by study staff to determine if the symptoms represent a treatment emergent adverse event. The blinded assessor will assess the prodrome and/or lesion and take measurements. More study product may be dispensed as needed. Most subjects' lesions will have resolved by day 7, and they will end study treatment after 7 full days of treatment. If lesion has not resolved by day 7, the maximum number of days the patient may use study drug treatment is 10 days.
 
The EOS is the final study visit will take place on Day 10. A photo will be taken of the irradiated area, the diary card will be carefully reviewed and study product (including empty containers) will be collected. If subjects reach EOS without full resolution of their lesion(s), they will be given the option to begin taking a prn medication for the remainder of the outbreak. Measurements will be taken. If an adverse event has occurred but has not resolved by the EOS visit, the subject will be contacted once weekly and status noted until such time as the event has resolved. The blinded assessor will assess the prodrome and/or lesion.
 
A Safety follow-up phone call will occur 2 days after the EOS to determine if any new AEs have occurred.
 
Safety will also be evaluated by an independent physician throughout the study. The first independent safety evaluation will be done once 5 subjects

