--	--

[figure not shown]
	have reached EOS. Thereafter, the independent safety evaluation will occur as each subsequent group of 5 subjects reaches EOS and will include data on all subjects having reached EOS.
Enrollment Period	Subjects will be enrolled over a 2 year period.
Treatment Period	Subjects will be treated for up to 7 days from the time they first experience a prodrome and/or a lesion. If lesion has not resolved by day 7, the maximum number of days the patient may use study drug treatment is 10 days. If subjects reach EOS without full resolution of their lesion(s), they will be given the option to begin taking a prn standard of care medication for the remainder of the outbreak. Subjects that do not exhibit a prodrome within 7 days of the induction visit, will be considered induction failures and be discharged from the study. Total time of study participation for any given subject may range from 13 to 25 days.
Location	University of Utah MidValley Clinic, Department of Dermatology
Safety Assessments	Solicited AEs by review of diary cards and discussion with subjects
Efficacy Assessments	Primary: 
Number of subjects that experience prodrome (Stage 1) but do not progress to vesicles (Stage 3) by completion of treatment Secondary: 
Subject-assessed duration of painClinician-assessed duration of lesion appearance (Stage 3), as reported by subject, to complete healing (Stage 5)Measurement of cumulative lesion area (all eruptions if more than 1)Measurement of each lesion (if more than one) from eruption (Stage 3) through healing of hard crust (Stage 4) to identify the largest lesion

TABLE OF CONTENTS

PROTOCOL SYNOPSIS	ERROR! BOOKMARK NOT DEFINED.
1. INRODUCTION	1
1.1 Background and Rationale	1
2. OBJECTIVE	2
2.1 Efficacy Endpoints	2
2.1.1 Primary:	2
2.1.2 Secondary:	2
2.2 Safety Endpoint	2
3. STUDY DESIGN	2
4. STUDY TREATMENT	4
4.1 EDTA Eye Drops	Error! Bookmark not defined.
4.2 Comparator: Abreva®	4
4.3 Randomization Codes	4
5. SUBJECT POPULATION	4
5.1 Inclusion Criteria	4
5.2 Exclusion Criteria	5
6. STUDY PROCEDURES	6
6.1 Study Visits	6
6.1.1 Screening Visit (Days -14 to 0)	6
6.1.2 Study Day 1 Visit (Baseline)	Error! Bookmark not defined.
6.1.3 Study Days 3 and 5 Visits	8
6.1.4 Study Day 7 +/- 1 day Visit	8
6.2 Study Day 10 Visit	Error! Bookmark not defined.
6.2.1 End of Study (EOS) Visit	Error! Bookmark not defined.
6.3 Early Discontinuation Visit	9
7. EFFICACY EVALUATIONS	9

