8. SAFETY EVALUATIONS

8.1 Adverse Events

8.1.1 Treatment Emergent Adverse Events

An adverse event (AE) or adverse experience is any untoward medical occurrence in a individual who is using the study product and that does not necessarily have a causal relationship with the study product but that occurs after the start of dosing and up to 2 days after the EOS visit. An AE can therefore be any unfavorable and unintended sign, symptom, or disease temporally associated with the use of the study product, whether or not considered related to it. Pre-existing conditions, which increase in frequency or severity or worsen in nature during or as a consequence of use of a drug in human clinical studies, will also be considered as adverse experiences.

An AE **does not** include:

- Medical or surgical procedures (e.g., surgery, endoscopy, tooth extraction, transfusion). The condition that leads to the procedure is the AE.
- Situations where an untoward medical occurrence has not occurred (e.g., hospitalization for elective surgery, social and/or convenience admissions).
- Worsening of symptoms associated with expected progression of periodontal disease are not considered an adverse event in this study

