8.1.2 Evaluation and Reporting of Adverse Events

All AEs (i.e. a new event or an exacerbation of a pre-existing condition) that occur after the start of dosing and up to 2 after the EOS visit, will be recorded as an AE or SAE (if applicable). (Any event occurring prior to start of treatment on Day 1 will be recorded as part of the subject's medical history.) All subjects who have used the study product at least once will be evaluated for safety.

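### Section 6.3 asks about new symptoms up to 7 days after the final visit, but the AE and SAE rules, synopsis and schedule stop at 2 days, so events starting on post-EOS days 3 to 7 have no recording rule

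*Combined protocol and SAP*

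**What the plan says.** Section 6.3 sets the calls: "Two days and seven days after the patient's final study visit, the study team will contact them". The subject is asked about unusual symptoms and, if there are any, "they may be asked to return to the clinic for an exam to determine if the symptoms are due to the study treatment".

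Section 8.1.1 limits an AE to an occurrence that "occurs after the start of dosing and up to 2 days after the EOS visit". Section 8.1.2 applies the same limit to what is recorded as an AE or SAE, with the unit missing: "after the start of dosing and up to 2 after the EOS visit". Section 8.1.3 builds the SAE definition on the AE definition.

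The synopsis (Design) has one call: "A Safety follow-up phone call will occur 2 days after the EOS to determine if any new AEs have occurred". The last column of the schedule in section 10 is the call at EOS+2 days. There is no column for a 7-day call.

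**The concern.** The protocol plans a safety contact whose findings its own definitions do not fully admit. Asking about symptoms and then examining the subject for a causal link to treatment is AE assessment in substance. If the symptom began after EOS+2, the plan does not say whether to record it, whether it can count as serious, or whether it goes into the AE listings.

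Adverse events are the only safety endpoint (section 2.2), and safety is part of the single objective (section 2). With 20 completers planned and AEs reported only in per-subject listings (section 9.3), one related late reaction left unlisted would visibly change the safety picture. The conflict over which calls take place adds a second problem: staff following section 6.3 and staff following section 10 would follow subjects for different lengths of time within the same clinic.

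**Working it through.** No sample-size or power figure is involved. The check sets the windows side by side on one time origin and counts days.

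**Time origin.** Section 6.3 counts from the final study visit; sections 8.1.1 and 8.1.2 count from EOS. Section 3 expects the EOS visit to be the final one, so the two origins coincide. Call that day 0.

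| Place | What it governs | Last post-EOS day reached |
|---|---|---|
| 6.3 | Symptom calls, possible causality exam | 7 |
| 8.1.1 | AE definition | 2 |
| 8.1.2 | Recording of AEs and SAEs | 2 (unit missing, read as days) |
| 8.1.3 | SAE definition, built on the AE | 2, inherited |
| Synopsis, Design | Safety call | 2 |
| Section 10 | Last schedule column | 2 |

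**Gap.** Days asked about but outside the definition: 7 − 2 = 5, namely post-EOS days 3, 4, 5, 6 and 7. That is 5 of the 7 post-EOS follow-up days.

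**Onset or discovery.** The limit in 8.1.1 and 8.1.2 depends on when the event occurs.
- Onset on post-EOS day 1, first mentioned at the 7-day call: within the window, recordable.
- Onset on post-EOS day 4, mentioned at the same call: outside the window, no rule.

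**Does another provision fill the gap?**
- The weekly contact after EOS (synopsis; sections 3 and 6.1.5) follows AEs that had already occurred and were unresolved at EOS. It does not cover new events.
- Section 8.1.4 starts a 24-hour clock when the investigator learns of an SAE and has no end date of its own. But an event must first be an SAE, and 8.1.3 leads back to the 2-day limit.
- Section 9.3 says when AE collection starts and not when it ends, so it does not override 8.1.1 and 8.1.2.

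**In days from last dose.** EOS is not the end of treatment for everyone. The schedule places the end of dosing at Day 7, while the text allows use up to Day 10 if the lesion is unresolved. With EOS on Day 10, the AE window closes on Day 10 + 2 = 12 and the second call falls on Day 10 + 7 = 17.
- Last dose Day 7: the window closes 12 − 7 = 5 days after dosing; the second call comes 17 − 7 = 10 days after.
- Last dose Day 10: the window closes 12 − 10 = 2 days after dosing; the second call comes 17 − 10 = 7 days after.

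If healing brings EOS forward, both limits move with it and the 5-day gap is unchanged.

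**The case against.** The strongest reply is that nothing in the protocol forbids recording a later event. Section 6.3 provides for an exam. Section 8.2 gives the independent clinician whatever safety information is available on subjects who have reached EOS, cumulatively. Sections 8.1.4 and 9.3 set no end date. This stands in part: a late event need not be lost. The supportable statement is that it lies outside the definition and the recording rule and its handling is unspecified, not that it will be discarded.

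It can also be said that the synopsis, 8.1.1, 8.1.2 and section 10 agree on 2 days, so deleting the 7-day call from 6.3 would remove the contradiction just as well. As a matter of consistency that is true. It would, however, give up a contact that the protocol already plans and that comes closer to covering late reactions in subjects who dose longest.

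Three stronger readings are tempting, and the documents do not support them.
- A reader might infer that anything learned at the 7-day call goes unrecorded. The limit is on onset, so events that began by EOS+2 remain AEs whenever they are mentioned.
- A reader might take the 5 of 7 days as post-treatment days. They are post-EOS days; the interval from last dose varies between subjects.
- A reader might infer that the synopsis range is wrong: "Total time of study participation for any given subject may range from 13 to 25 days". The upper end can be read as 14 (screening) + 9 (Day 1 to Day 10) + 2 = 25, which leaves out the wait for a prodrome and the 7-day call. It can equally be read as 1 (induction day) + 7 (prodrome wait) + 10 (Days 1 to 10) + 7 (second call) = 25, which includes both. No start point is given, so the range neither shows an error nor settles which call schedule is meant.

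**Conclusion.** The contradiction is real and rests on the text alone. Section 6.3 conflicts with the synopsis and section 10 on whether a 7-day call takes place, and with 8.1.1 to 8.1.3 on whether a new event found at that call counts. The size is 5 post-EOS days of onset for each subject followed to the 7-day call.

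This rests on two readings: that the final study visit and EOS are the same day, and that the missing unit in 8.1.2 is days. Both are well supported by the surrounding text. The documents give no rate of late reactions, so the number of events affected cannot be estimated. In a pilot with 20 completers and listings only, the effect on the analysis is likely to be modest. The correction should still be made, because the gap falls on the only safety endpoint and is inexpensive to close.

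**What to change.** Reconcile the synopsis and sections 6.3, 8.1.1, 8.1.2 and 10 to one safety follow-up window:

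1. In 8.1.1 and 8.1.2, extend AE and SAE recording to the 7-day call already planned in 6.3, and supply the missing unit in 8.1.2. Section 8.1.3 then inherits the longer window without a change of its own.
2. Add an EOS+7 column to section 10, with AE solicitation and concomitant medications.
3. Name both calls in the synopsis.

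Optionally, state the start point of the participation range in the synopsis so that it can be checked against the final schedule. The figures themselves need no change on the present evidence.

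The cost is wording and one schedule column; no new contact is added to what 6.3 already requires. The downside is that a few more unrelated AEs may appear in the listings.

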7. EFFICACY EVALUATIONS

7.1 Number of subjects that experience prodrome (Stage 1) but do not progress to vesicles (Stage 3) by completion of treatment

The Principal Investigator or his designee will review all photographs taken from Day 1 through the EOS visit against the onset of prodrome date and the date of healing or 7 full days of treatment noted on the subject's diary card. They will then determine the duration of the HSV outbreak (prodrome to healed). This may or may not agree with the subject's assessment of "healed" but should be based on the collective information gathered during the subject's time on study. The blinded assessor will assess the prodrome and/or lesion at every clinic visit starting at day 3. The blinded assessor will only be responsible for the rating of the prodrome and or/lesions. The blinded assessor will not be performing safety evaluations. The unblinded staff will instruct the subject to not talk with the blinded assessor about which treatment they have been using.

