3. STUDY DESIGN

This will be a randomized, efficacy assessor-blinded, parallel group, pilot study of up to 20 subjects with documented UV induced herpes labialis. We will enroll until we have 20 subjects that have expressed a lesion from the induction and complete the treatment period of the study. With the possibility of screen failures and induction failures, we may consent up to 35 patients maximum.

Potential subjects will be assessed during a screening visit that must take place no greater than 2 weeks prior to the Induction visit. During the screening period, subjects that meet all other entry criteria will undergo UV susceptibility testing to determine their individual MED (minimal erythema dose). UV susceptibility testing takes place over two days with exposure to UV light on specified regions on the subject's back followed by an assessment of the exposed areas 24 hours later to identify the MED.

Subjects who have a measurable MED will be allowed to enroll in the study. Each subject will be randomly assigned in a 1:1 ratio to receive either EED or Comparator.

Subjects that do not have a measurable MED will be considered screen failures or may have repeat MED testing with new values.

At the Induction Visit, subjects will undergo UV radiation at a level 3 times their MED. The exposed area of the lip will be marked with indelible ink and a baseline photograph may be taken.

Each subject will then be randomly assigned in a 1:1 ratio to receive either EED or Comparator. Subjects will be dispensed study medication and instructed how to apply it to the exposed area. Dosing of the study product will be done 5 times daily, beginning at the time that a subject first senses the start of the prodromal phase (Day 1). The EED is a clear viscous eye drop, and the Comparator is a white cream substance. Therefore, the subject and principal investigator will be unblinded, and only efficacy assessments will be done by a qualified trained blinded assessor.

Subjects will be given a diary card to record their pain levels (starting at Day 1), progression of lesion development and any unusual symptoms (not normally seen with their outbreaks).

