4.3 Randomization Codes

A simple randomization code will be generated by the Investigator so that subjects are randomly assigned in a 1:1 ratio to either EED or Abreva.

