9.2 Efficacy Analysis

The proportion of patients with nonulcerative recurrences which do not progress to vesicles (Phase 3) will be compared between treatment groups using a χ^2 test. The episode duration and lesion size parameters will be compared between the treatment groups with a two-sample Student t-test. The time to lesion healing will be assessed using Kaplan-Meier methods. To illustrate the total clinical benefit of EED, an analysis of time to lesion healing and lesion area for all recurrences (i.e., including both ulcerative lesions and nonulcerative recurrences) will be performed as “all lesions.” In this analysis, the impact of prevention of ulcerative lesions will be introduced by assigning zero values to nonulcerative recurrences.

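### Section 7.1 lets the unblinded PI, or a designee of unstated blinding, determine outbreak duration, although Section 3 gives efficacy assessment to a blinded assessor

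*Combined protocol and SAP*

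**What the plan says.** Section 3 explains that the two products look different, and concludes that "the subject and principal investigator will be unblinded, and only efficacy assessments will be done by a qualified trained blinded assessor".

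Section 7.1, which stands under Efficacy Evaluations, gives a different person the duration call: "The Principal Investigator or his designee will review all photographs taken from Day 1 through the EOS visit", comparing them with the diary's prodrome and healing dates. Next comes "They will then determine the duration of the HSV outbreak (prodrome to healed". The result need not match the subject's own opinion of healing, and it "should be based on the collective information gathered during the" subject's participation. The same section confines the blinded assessor to rating the prodrome and lesions.

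Duration is an efficacy outcome. Section 2.1.2 lists lesion duration until loss of the hard crust as a secondary endpoint. The synopsis (Efficacy Assessments) describes it as assessed by a clinician, from Stage 3 as the subject reports it to Stage 5, and does not say that the clinician is blinded. Section 9.2 plans two analyses: "The episode duration and lesion size parameters will be compared between the treatment groups with a two-sample Student t-test" and "The time to lesion healing will be assessed using Kaplan-Meier methods".

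**The concern.** Subjects know which product they use, and so does the PI. Blinded rating is therefore the main protection against assessment bias in the lesion outcomes, and it is what the title's efficacy assessor-blinded label promises. Whether a lesion has healed is a judgement, and Section 7.1 says openly that the study's judgement may depart from the subject's. If a person who knows the arm makes it, expectations about either product can enter the between-arm comparison of duration, and the analysis cannot remove them afterwards. The trial exists to collect preliminary efficacy data, so a duration difference that may partly reflect the reader's knowledge of treatment would be hard to interpret.

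**Working it through.** The plan attaches no figure to this point, so there is none to reproduce. The check is a comparison of texts, followed by a small sensitivity calculation.

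**Who decides, and is that person blinded?**

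| Step | Person named | Blinding | Where |
|---|---|---|---|
| Rating of prodrome and lesion | Blinded assessor | Blinded | Synopsis (Design), 7.1, 10 |
| Review of photographs against diary dates | PI or designee | PI unblinded; designee not stated | 3, 7.1 |
| Outbreak duration, prodrome to healing | PI or designee | As above | 7.1 |
| Lesion duration, Stage 3 to Stage 5 | A clinician | Not stated | Synopsis (Efficacy Assessments) |

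**Does the call reach an analysed outcome?**

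1. Section 9.2 does not define episode duration. The candidates are prodrome to healing (7.1) and Stage 3 to Stage 5 (synopsis).
2. The two start at different points, but both end at healing.
3. The Kaplan-Meier analysis also has healing as its event.
4. The only determination of healing that 7.1 describes belongs to the PI or designee. No section says that the blinded ratings supply the healing date.
5. So a person who knows the arm may set the end date for the t-test and the Kaplan-Meier analysis. *May* is the right word, because the documents do not say which date is used.

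**Is the start of blinded rating consistent?** Section 7.1 starts it at Day 3. The synopsis (Design) and the Section 10 schedule have it at Day 1.

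**Sensitivity of the mean.** This is not an estimate of bias.

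- Inputs: 20 subjects planned (Sections 3 and 5) and 1:1 allocation. Assumption: 20 / 2 = 10 per arm, all contributing a duration.
- Formula: change in arm mean = (days moved × subjects moved) / n contributing in that arm.
- One subject moved by 1 day, n = 10: 1 × 1 / 10 = 0.1 day.
- The same with n = 6, as an illustration of fewer contributors: 1 / 6 = 0.17 day.

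Fewer than 10 is likely if episode duration means Stage 3 to Stage 5, because a subject who never reaches Stage 3 has no such interval. A subject unhealed at the Day 10 visit has no observed healing date either.

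**The case against.** - **The Section 3 sentence is ambiguous.** Its *only* can be read as limiting the assessor to efficacy work, which 7.1 supports by keeping the assessor away from safety evaluations. Nor can every efficacy measure belong to the assessor, since subjects rate their own pain. This stands in part: the conflict is less absolute than a flat contradiction. But duration is a clinician's judgement under Efficacy Evaluations, and on either reading 7.1 permits the unblinded PI to make it.
- **The designee could be blinded.** That is possible but not required. The designee cannot be presumed to be the existing blinded assessor, because 7.1 restricts that role to rating.
- **Blinded ratings could supply the healing date.** The synopsis equates complete healing with Stage 5, which a lesion rating could capture. That would be a good arrangement, but no section adopts it.
- **The 7.1 interval is not a listed endpoint.** This stands. The listed endpoint is lesion duration, so the link to an analysed outcome runs through the shared healing date and the undefined term in 9.2.
- **A reader might infer that the primary outcome is also judged unblinded**, because 7.1 carries the primary endpoint's title. The documents do not support this. Lesion rating is repeatedly given to the blinded assessor, and nothing gives the PI the Stage 3 call. What is true is only that 7.1 does not say whose rating decides Stage 3. For that reason no figure is given here for the primary proportion, or for the analysis in 9.2 that sets nonulcerative recurrences to zero.
- **A reader might also infer that the assessor's blind is broken at visits**, since product containers are checked or collected there. The text is silent on the order of steps. Sections 6.1.3 and 6.1.4 give the container checks to study staff, and 7.1 has subjects told not to discuss treatment with the assessor.

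**Conclusion.** The concern holds for outbreak duration and the healing date. As written, the plan allows a person who knows the arm to make a discretionary judgement of healing that may feed an analysed secondary outcome. Confidence is high that the sections need reconciling. It is lower that the 7.1 date is the one analysed, because 9.2 leaves the interval undefined.

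The size and direction of any bias cannot be derived from the documents. The 0.1 day per subject-day rests on 10 contributors per arm and shows only how little averaging a pilot of this size provides. It does not show that bias will occur. The point should be fixed, but it does not undermine the primary comparison.

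**What to change.** 1. In 7.1, have the blinded assessor set the healing date, and confirm Stage 3, from the visit ratings and the available photographs coded to hide treatment. Amend the sentence that limits the assessor to rating.
2. Have unblinded staff pass on the diary's prodrome-onset date and any subject-reported dates, without treatment information. Calculate duration from these dates.
3. Remove the PI from this determination, or require the designee to be blinded to treatment.
4. In 9.2, state which interval episode duration is.
5. Reconcile the start of blinded rating between 7.1 (Day 3) and the synopsis and Section 10 (Day 1).

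Keeping product handling apart from rating at visits is an optional further safeguard.

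The cost is protocol wording and slightly more work for an assessor the trial already has. Some limits remain. Prodrome onset, and events between visits, still come from unblinded subjects. Photographs may be incomplete for virtual visits: Sections 6.1.3 to 6.1.5 commit to them when the subject is in clinic but leave subject uploads optional.

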6.1.4 Study Days 3, 5, and 7 Visits

On Days 3, 5, and 7, the subject will present for a follow up appointment in clinic or via virtual video call consisting of:

- Review of the subject’s diary card to identify possible treatment emergent adverse events.
- Assessment of the subject’s pain on a visual analog scale.
- Measurement of the lesion will be taken (if lesion is present).
- Photographs of area exposed to UV radiation may be asked to be taken by subjects and uploaded into their MyChart account. If patients are present in clinic, photographs will be taken by study staff.
- If the subject has experienced a prodrome or lesion they should have started dosing. The study staff will review their dosing compliance and examine the study product tube/bottle. If the subject is not complying with the dosing regimen, the study staff will determine whether non-compliance is serious enough to warrant terminating the subject’s participation. Otherwise, minor non-compliance should be noted, and the subject should be retrained on how to dose themselves.

Once patients reach the Stage 2/3 lesion their lesion may be swabbed for viral culture (HSV PCR). If the patient reaches Stage 2/3 over the weekend, the lesion will not be swabbed. We will reserve this for the first five patients but may continue to do all patients to ensure lesion is in fact a cold sore and not a reaction to the UV radiation.

6.1.5 EOS – End of Study Visit (Day 10 – or after subject’s lesion has fully healed)

An EOS visit will occur after the subject’s lesion has fully healed or Day 10 (whichever comes first), the subject will present to the clinic for a follow up appointment in clinic or via virtual video call consisting of:

- Review of the subject’s diary card to identify possible treatment emergent adverse events. If the subject has an AE that has not resolved by this time, the site staff will explain to the subject that they will be called every week to check on the status of the AE, until it is resolved.
- Assessment of the subject’s pain on a visual analog scale.

- Photographs of area exposed to UV radiation may be asked to be taken by subjects and uploaded into their MyChart account. If patients are present in clinic, photographs will be taken by study staff.

The subject's diary card and all tubes//bottles of study product (empty, partially used or unused) will be collected and the subject will be released from the study.

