10. SCHEDULE OF ASSESSMENTS

ASSESSMENT	SCREENING	Induction Visit	Daily after induction visit to Day 1	DAY 1	DAY 5	DAY 7	DAY 10/ EOS	Follow -up phone call (EOS +2 days)
Informed Consent	X							
Medical/HSV History	X	X (med hx only)						
Urine Pregnancy Test (for woman of child bearing potential only)	X							
Limited Physical Exam	X	X						
Concomitant Medications	X	X						X
UV susceptibility test / MED testing	X (exposure)							
MED Reading		X						
Randomization		X						
UV exposure at 3 x MED (cold sore inducing)		X						
Study Product Dispensed		X						
Dosing Begins				X				
Dosing Ends						X		
Collect Study Product (including empty tubes/bottles)							X	
Photograph of irradiated area and lesion may be taken		X		X	X	X	X	X
Measurement of lesion (if possible)				X	X	X	X	X
Dispensing of Diary Card		X						
Review of Diary Card/Dosing compliance				X	X	X	X	
Solicitation of Adverse Events			X	X	X	X	X	X
Rating of lesion by blinded assessor				X	X	X	X	
Phone call to check for prodromal senses			X

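### Section 7.1 restricts the blinded assessor to rating while the synopsis has that assessor also measure, so the plan allows, without directing, unblinded measurement of two of the four secondary endpoints

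*Combined protocol and SAP*

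**What the plan says.** All references are to the combined protocol and SAP.

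- **Section 7.1** defines the role narrowly: "The blinded assessor will only be responsible for the rating of the prodrome and or/lesions". The sentence before it sets the start: "The blinded assessor will assess the prodrome and/or lesion at every clinic visit starting at day 3". The sentence after it reads "The blinded assessor will not be performing safety evaluations".
- **Synopsis, Design**, once for Day 1 and again for Days 3, 5 and 7: "The blinded assessor will assess the prodrome and/or lesion and take measurements". For the end-of-study (EOS) visit it says "Measurements will be taken" and names nobody; the blinded assessment at that visit is a separate sentence.
- **Section 3** explains that the products look different, so the subject and principal investigator know the arm, and that "only efficacy assessments will be done by a qualified trained blinded assessor". Its paragraph on the Day 1, 3, 5 and 7 visits has the subject follow up with the blinded assessor. That same paragraph covers diary review, the compliance check, lesion measurement and dispensing.
- **Sections 6.1.3 and 6.1.4** call for the lesion to be measured when one is present, without saying by whom. **Section 6.1.5** (EOS) has no measurement item.
- **Section 10** has a row titled "Rating of lesion by blinded assessor" and a separate measurement row with no assessor named. The measurement row is also marked at the follow-up call two days after EOS; the rating row is not.

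**The concern.** The two products cannot be made to look alike, so the design relies on a blinded assessor to protect the efficacy data. Where a lesion ends is a judgement, and a measurer who knows the arm can lean one way without meaning to.

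Section 2.1.2 lists four secondary endpoints. Two of them, cumulative lesion area and maximum lesion size, come directly from these measurements. Section 9.2 compares lesion size parameters by two-sample t-test and uses lesion area again in the all-lesions analysis.

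The other two secondary endpoints are less well protected in any case. Pain is rated by the subject, who knows the arm. Section 7.1 leaves outbreak duration to the principal investigator, who also knows it, or a designee. Area and size are therefore the secondary endpoints that a blinded measurer can most readily protect.

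**Working it through.** The plan states no figure to reproduce. The main check is a comparison of text, followed by an illustrative calculation.

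**Step 1. Who measures, place by place**

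| Place | Who rates | Who measures |
|---|---|---|
| Synopsis, Day 1 and Days 3, 5, 7 | Blinded assessor | Blinded assessor |
| Synopsis, EOS | Blinded assessor | Not named |
| Section 3, blinding statement | Blinded assessor (efficacy assessments) | Blinded assessor, if measuring counts as an efficacy assessment |
| Section 3, Day 1 to 7 visits | Visit is with the blinded assessor | Not named, but in the same paragraph |
| 6.1.3 and 6.1.4 | Not named | Not named |
| 6.1.5, EOS | Not named | No measurement listed |
| 7.1 | Blinded assessor, from Day 3 | Outside the role, if *only* is read literally |
| Section 10 | Blinded assessor, from Day 1 | Not named |

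Two conflicts follow: whether the role includes measuring (7.1 against the synopsis), and whether it starts on Day 1 or Day 3 (7.1 against the synopsis and Section 10). No row assigns measuring to unblinded staff. Nothing in Sections 6 or 7 or the schedule requires the measurer to be blinded.

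**Step 2. Endpoints affected**

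Section 2.1.2 lists pain, lesion duration, cumulative area and maximum size. Area and size rest on measurement: 2 of 4.

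**Step 3. Illustration of what unblinded measuring could do**

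Inputs:
- From the documents: 20 subjects allocated 1:1, two-sample t-test.
- Assumed: exactly n = 10 per arm; two-sided 5% level; between-subject coefficient of variation (CV) of 50 to 70%; no true effect; a proportional measuring difference b between arms of 10, 20 or 30%.

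Formulas: standardized shift d = b / CV; noncentrality = d × √(n/2) = d × √5 = 2.236 d; degrees of freedom = 2 × 10 − 2 = 18. The false-positive rate is the probability that a noncentral t variable with these values falls beyond ±2.101, counting both tails.

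| b | CV 70%: d, noncentrality, rate | CV 50%: d, noncentrality, rate |
|---|---|---|
| 0% | 0, 0, 5.0% | 0, 0, 5.0% |
| 10% | 0.14, 0.32, 6.1% | 0.20, 0.45, 7.1% |
| 20% | 0.29, 0.64, 9.3% | 0.40, 0.89, 13.6% |
| 30% | 0.43, 0.96, 14.8% | 0.60, 1.34, 24.6% |

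The calculation covers a t-test on measured lesions. It does not model the all-lesions analysis in 9.2, where nonulcerative recurrences are set to zero and those zeros cannot carry measuring bias.

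**The case against.** A reader might infer that the protocol plans for unblinded staff to size the lesions. The documents do not support that. The synopsis says twice that the blinded assessor measures, Section 3 gives efficacy assessments to that assessor, and its visit paragraph puts lesion measurement within a visit held with that assessor. No passage assigns measuring to anyone unblinded.

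The word *only* in 7.1 may be meant just to keep the assessor off safety work, since the next sentence excludes safety evaluations. Section 7.1 is also headed for the primary endpoint, and Section 7 has no subsection on lesion size, so its silence on measuring is weak evidence. Separate rows in Section 10 do not imply separate people. The measurement mark two days after EOS falls on a phone call, which 6.3 describes only as asking about symptoms, so it may be a stray mark.

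The error rates depend on a CV, a bias and a significance level that the documents do not give. Equal arms are not guaranteed either, because 4.3 specifies simple randomization. Finally, this is a pilot and these are secondary endpoints.

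All of this stands, and it makes blinded measurement the probable intent. It does not remove the conflict. Read literally, 7.1 leaves measuring outside the blinded role, and the visit sections and schedule that a site works from do not put it back.

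**Conclusion.** The inconsistency is real and should be corrected. The plan as written allows, but does not direct, unblinded measurement of cumulative lesion area and maximum lesion size, 2 of the 4 secondary endpoints. Under 7.1 the Day 1 measurement has no blinded assessor at all.

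The textual finding needs no numerical assumption. The effect on error rates is illustrative only: under the assumptions above, about 6 to 7% for a 10% measuring difference, 9 to 14% for 20% and 15 to 25% for 30%, against a nominal 5%. The documents give no sign that a difference of any such size would arise.

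The measurement conflict does not reach the primary endpoint, which rests on lesion stage. From Day 3 on, the rating is the blinded assessor's task under 7.1, the synopsis and the schedule alike.

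**What to change.** 1. **Section 7.1.** Replace the sentence containing *only* with: *The blinded assessor will be responsible for rating the prodrome and/or lesions and for all lesion measurements, and for no safety, compliance or dispensing task.* Change the start from Day 3 to Day 1, to match the synopsis and Section 10.
2. **Name the measurer.** State that the blinded assessor measures in 6.1.3, 6.1.4, the synopsis sentence on EOS and the measurement row of Section 10. Add an EOS measurement by the blinded assessor to 6.1.5, since the synopsis and schedule already call for one.
3. **Section 3, Day 1 to 7 visits.** Assign diary review, the compliance check and dispensing to unblinded staff, separately from the blinded assessment. The compliance check in 6.1.3 and 6.1.4 includes examining the tube or bottle, which would reveal the arm.
4. **Section 10, follow-up call.** Remove the measurement mark or reconcile it with 6.3.
5. **Section 9.2.** State that only measurements made by the blinded assessor enter the area and size analyses.

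The cost is a few words in each of these places. No new staff, visit or procedure is needed, because the synopsis, Section 3 and the schedule already have the blinded assessor at these visits. The small downside is that any measurement taken by someone else is left out of the area and size analyses.
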